Heart transplant patients with CAV who primary transplant followup care at the University of Nebraska will serve as the study cohort. Given the complexity of heart transplant patients, care is highly-protocolized and organized according to graft age. Care is most intensive in the first year following transplant wherein patients are initially evaluated on a weekly basis for the first month with reduced frequency (biweekly \rightarrow monthly \rightarrow quarterly) based on clinical progress over the first year. During year 2 post transplant, stable post-transplant patients are typically seen quarterly and this extends to biannual evaluations during year 3. After 3 years, stable post-transplant patients can often be seen on an annual basis. Thorough evaluations are completed annually including comprehensive labwork (complete blood count, complete metabolic panel, fasting lipid panel, thyroid function tests, hemoglobin A1c, creatinine kinase, urine protein analysis), assessment for donor specific antibodies, and imaging/testing. Imaging/testing includes an annual echocardiogram and chest x-ray as well as other imaging (DEXA scan, carotid and abdominal ultrasounds) at frequencies determined by comorbidities. Immunosuppression is maintained with calcineurin inhibitors (primarily tacrolimus) and DNA synthesis inhibitors (mycophenolate mofetil, mycophenolic acid or azathioprine). Patients are switched to mTOR inhibitors (primarily sirolimus) if significant renal dysfunction develops or CAV is diagnosed. High dose steroids are started at the time of transplant and typically weaned off during the first year. Calcineurin inhibitors and mTOR inhibitors are dosed according to trough serum levels, and thus monitored at least every three months indefinitely.

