Study participation is expected to coordinate with the standard care of heart transplant patients. As most patients with CAV are more than 2 years post-transplant, enrollment will likely occur around the patient's annual clinical evaluation. Female patients of childbearing potential will undergo pregnancy testing prior to or during the screening/enrollment visit before study drug administration. Informed consent and baseline documentation will be completed by research personnel at the patient's annual evaluation when feasible.

Enrolled study participants will be treated with evolocumab (Repatha) 140 mg injected subcutaneously every 2 weeks for 52 weeks. All study participants will receive instruction on correct self-administration by research pharmacists. Study drug will be distributed to patients via courier or Fed Ex temperature-controlled coolers by the research pharmacy. The evolocumab dose (140 mg every 2 weeks) will remain constant for the duration of the study. Side effects will be assessed on a quarterly basis. Serious adverse events considered related to treatment, death, and pregnancy will all result in immediate discontinuation of the study drug.

Primary endpoint – LDL percentage change after 12 weeks of evolocumab therapy.

The primary objective of this study is to measure the impact of PCSK9 inhibition via evolocumab on serum LDL in heart transplant patients with CAV after 12 weeks. Similar to prior phase 2 trials investigating evolocumab, LDL change will serve as the primary endpoint providing a direct benchmark for comparison of heart transplant

patients. Baseline LDL will be obtained at study enrollment, likely with the patient's annual clinical evaluation. After 12 weeks of therapy, a fasting serum lipid profile will be obtained for measurement of LDL and assessment of the primary endpoint. Statistical analysis is detailed in Section 8 below.

Secondary endpoints

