Assess the effect of evolocumab on CAV progression. All patients enrolled will have CAV documented by cardiac angiography. Standard post-transplant care includes annual angiograms in patients diagnosed with CAV to monitor for disease progression. CAV progression will be defined as an increase of one CAV grade (CAV-1 \rightarrow CAV-2 or CAV-2 \rightarrow CAV-3). The number of patients with CAV progression of at least one grade while on evolocumab will be compared to historical controls for our transplant program. Percentage diameter stenosis for each vessel with visible CAV also will be determined by quantitative coronary angiography (QCA) using Philips Xcelera software package in a blinded fashion by an experience interventional cardiologist for patients angiograms completed one year prior to study entry, at study entry, and study conclusion. Angiographic change while on evolocumab therapy will be compared to the preceding year.

Assess the effect of evolocumab on immunosuppression regimens and graft rejection. Transplant patient are maintained on lifelong immunosuppression. These agents are prone to significant drug-drug interactions which can limit therapies. Serum levels of immunosuppression are monitored every three months per standard protocol. Measured serum levels at 3, 6, 9, and 12 months, as well as the number of dose adjustments while on evolocumab therapy while on evolocumab therapy will be compared to the preceding year. Statistical adjustment for confounding factors such as changes in renal function or other drugs known to alter immunosuppression levels (i.e. diltiazem, certain antimicrobial drugs) will be completed. In addition, the incidence of transplant rejection will be documented while on evolocumab therapy and compared to the prior year. Transplant rejection will be defined as symptoms requiring therapeutic intervention or endomyocardial biopsy findings of ≥grade 2 or positive C4d staining or new donor specific antibodies.

Measure the effect of evolocumab on serum lipids including HDL and triglycerides after 1 year of therapy. Fasting lipid profiles (total cholesterol, LDL, HDL and triglycerides) after 52 weeks of evolocumab therapy will be compared to baseline levels. Fasting lipid profiles are assessed annually as part of routine post-transplant care. The percentage change of LDL, HDL and triglyceride from baseline will be calculated after 1 year of evolocumab therapy.

Statistical analysis is detailed in Section 8 below.

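### The raw count of immunosuppressant dose adjustments is not comparable with the preceding year for patients entering less than about 24 months after transplant, or for those who stop treatment early

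*Combined protocol and SAP*

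**What the plan says.** Under Secondary endpoints, in the paragraph on immunosuppression regimens and graft rejection, the protocol compares serum levels at 3, 6, 9 and 12 months with the year before, and adds: "as well as the number of dose adjustments while on evolocumab therapy while on evolocumab therapy will be compared to the preceding year". The same paragraph promises adjustment for confounders and gives changes in renal function and interacting drugs as examples. Graft age and number of checks are not mentioned.

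Section 8 has a linear mixed model for serum levels from baseline onward, a McNemar test for CAV progression, and paired tests of continuous secondary endpoints against baseline. None of these is a stated method for a count set against the preceding year.

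Standard post-transplant care describes two different frequencies:

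- **Clinic visits** decline with graft age. "Care is most intensive in the first year following transplant wherein patients are initially evaluated on a weekly basis for the first month", then less often through that year. In year 2, "stable post-transplant patients are typically seen quarterly and this extends to biannual evaluations during year 3". Later, "After 3 years, stable post-transplant patients can often be seen on an annual basis".
- **Trough levels** have a floor at every graft age: "Calcineurin inhibitors and mTOR inhibitors are dosed according to trough serum levels, and thus monitored at least every three months indefinitely".

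The same section says that patients are moved to an mTOR inhibitor when CAV is diagnosed or significant renal dysfunction develops. On graft age at entry, the section on patient enrollment says only: "As most patients with CAV are more than 2 years post-transplant". The eligibility criteria set no minimum.

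**The concern.** These drugs are dosed from trough levels, so a dose changes mainly when a level or visit prompts it. A raw count therefore depends on how many such occasions each year contains, and on how long the year of observation lasts.

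The first post-transplant year has many more occasions than any later year. CAV can be found at the first annual catheterization, and enrollment is expected around the annual evaluation, so the plan allows a patient's preceding year to be wholly or partly that first year. For such a patient the evolocumab year would show fewer adjustments even if the drug did nothing.

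A second mechanism applies at any graft age. The protocol requires study drug to stop for related serious adverse events, death or pregnancy. A count taken on treatment over a shortened period would then be set against a full preceding year.

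The endpoint exists to detect a drug interaction that makes immunosuppression harder to manage. Both mechanisms push towards false reassurance on that question.

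**Working it through.** The plan states no figure for this comparison, so there is none to reproduce. The check counts scheduled trough checks before and after entry and then averages over a cohort.

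**Inputs from the documents.** Trough checks are at least every 3 months, so 4 a year is the floor. First-year visits are weekly for a month, then biweekly, monthly and quarterly. Most patients with CAV are past 2 years.

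**Assumptions.** The documents do not say when first-year visits move from one frequency to the next. I took biweekly visits to month 2, 3 or 6 and monthly visits to month 6, 9 or 12, with a level at each first-year visit. The four combinations tried give 12, 13, 15 and 20 checks in that year. Adjustments are taken as proportional to checks. After the first year the 4-a-year floor is used.

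**Step 1: scheduled trough checks by time of entry.**

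| Entry after transplant | Preceding 12 months | Next 12 months |
|---|---|---|
| 12 months | 12 to 20 | 4 |
| 15 months | 6 to 13 | 4 |
| 18 months | 4 to 8 | 4 |
| 21 months | 4 to 6 | 4 |
| 24 months or later | 4 | 4 |

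The imbalance is confined to entry before about 24 months and shrinks quickly after 12. Clinic visits keep falling later (4 versus 2 for entry at 24 months, 2 versus 1 at 36), but the trough schedule does not.

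**Step 2: cohort average.** Let f be the share of enrollees whose preceding year is the whole first post-transplant year, with V checks in it. Everyone else has 4 before and 4 after.

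- Mean checks in the preceding year: P = f × V + (1 − f) × 4
- Apparent change with no drug effect: 4/P − 1
- True rise in adjustments per check that would look like no change: P/4 − 1

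| f | P at V = 12 and 20 | Apparent fall | Rise that would be masked |
|---|---|---|---|
| 0% | 4.0 and 4.0 | 0% | 0% |
| 5% | 4.4 and 4.8 | 9% to 17% | 10% to 20% |
| 10% | 4.8 and 5.6 | 17% to 29% | 20% to 40% |
| 20% | 5.6 and 7.2 | 29% to 44% | 40% to 80% |

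Example at f = 10%, V = 12: P = 0.10 × 12 + 0.90 × 4 = 4.8; 4/4.8 − 1 = −16.7%; 4.8/4 − 1 = +20%. With n = 40, f = 10% is 4 patients.

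**Step 3: shortened treatment.** At a constant adjustment rate, a patient who stops at week 26 of 52 is expected to have 26/52 = 50% of the preceding year's count. Dividing by time on treatment removes this.

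**Step 4: after restriction.** For patients entering at 24 months or later, scheduled checks are 4 and 4. The ratio is 1.0 and the schedule-driven fall is 0%.

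**The case against.** The best case against the point is that the declining schedule is for clinic visits, whereas calcineurin and mTOR inhibitors are dosed from trough levels on a three-monthly floor. Recruitment draws on more than 40 patients with an existing CAV diagnosis, most of them past 2 years. The confounder list is open-ended, the count is read beside serum levels at fixed times, and the plan calls its secondary endpoints primarily hypothesis-generating.

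Much of this stands. A reader might infer that the count falls by schedule across the whole cohort. The documents do not support that: for entry at 24 months or later, scheduled checks are equal. Extra unscheduled checks are possible, because the floor is only a minimum, but they cannot be sized.

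A reader might also infer that the bias always runs towards fewer adjustments on evolocumab. That fails too. In a patient diagnosed with CAV and enrolled soon after, the mTOR switch and the dose changes that follow can fall in the treatment year and raise the count. The adverse-event contacts at weeks 2, 4, 12, 26, 38 and 52 exist only in that year and might prompt changes as well.

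A third inference is that first-year steroid weaning inflates the comparator. The documents do say "High dose steroids are started at the time of transplant and typically weaned off during the first year", but the dose-adjustment sentence follows directly on drugs monitored by serum level. Nothing says weaning steps are counted.

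What the objection does not remove is the minority with young grafts. The plan admits them, and neither the endpoint text nor Section 8 says how their first-year comparator will be handled. An open-ended promise to adjust does not settle this, because graft age is not named and no model for the count exists.

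**Conclusion.** The point holds for a limited group. The stated comparison is confounded for patients whose preceding year reaches into the first post-transplant year, and for anyone whose treatment is cut short. It is sound as regards monitoring schedule for patients entering at 24 months or later who complete treatment.

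The size cannot be determined from the documents. It depends on an assumed share of young grafts, an assumed number of first-year checks, and adjustments being proportional to checks. It is zero if no one enters with a first-year comparator. The figures for 5% to 20% of enrollees illustrate what could happen and do not estimate this cohort. They also assume a full first-year comparator, which requires entry at about 12 months. The net direction is open because of the mTOR switch, so the firm conclusion is that the raw count would be hard to interpret in these patients, whichever way it moves.

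The consequence is moderate. This is a secondary, hypothesis-generating comparison, but it addresses a safety-relevant question and the remedy is cheap.

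**What to change.** Change the immunosuppression paragraph under Secondary endpoints, and add the matching method to Section 8:

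1. Base the main comparison on patients whose preceding year starts after the first post-transplant year, that is, entry at 24 months or later. List the others separately with their time since transplant. Dividing by time does not cure the first-year problem, so this restriction is needed as well as item 2.
2. Define the endpoint as calcineurin and mTOR inhibitor adjustments per patient-time, using actual time on evolocumab against the preceding year. Name a paired count model, for example Poisson or negative binomial with a patient effect and log time as offset.
3. Flag adjustments that belong to an mTOR switch made under the programme's protocol, and show results with and without them.
4. Give adjustments per level drawn only as a sensitivity analysis. An interaction may itself prompt extra levels: going from 2 adjustments in 4 levels to 4 in 8 doubles the count but leaves the rate per level at 0.5.

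The cost is SAP wording, plus transplant dates, treatment dates and level counts, which should already be in clinic and study records. The downside is that a few young-graft patients leave this one comparison; on the protocol's own statement about graft age, most patients stay in.

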All suspected unexpected serious adverse reactions (SUSARs) related or possibly related to evolocumab and their follow-up reports will be reported to Amgen within 24 hours of submission to the regulatory agency or IRB. Amgen will be informed of any pregnancy occurring and/or existing during exposure to the investigational medicinal

product and pregnancies occurring in the partner of a patient participating in the study and potential infant exposure within ten (10) calendar days of sponsor awareness.

Section 8. Statistical Analysis Plan

Statistical analysis will be completed with the direct assistance of faculty from the University of Nebraska biostatistics department. Sample size (n=40) is chosen based on the size of the heart transplant clinic (the number of heart transplant patients with CAV expected to be eligible for study participation).

The primary outcome is percentage change from the baseline in LDL levels after 12 weeks of evolocumab therapy. Prior trials have demonstrated that evolocumab lowers LDL cholesterol at week 12 by greater than 50% from baseline[2, 3]. The sample size of n=40 is expected to yield greater than 99% power to detect 50% reduction of LDL cholesterol from baseline after 12 weeks of evolocumab therapy at a significance level of 0.05 using a two-sided Wilcoxon signed-rank test, assuming the estimated standard deviation of reduction of 0.17.

Descriptive statistics will be presented as frequencies and percentages for categorical variables, and mean ± standard deviation, or median with range for continuous variables, unless otherwise indicated. Paired t-tests or Nonparametric Wilcoxon signed-rank tests will be completed where appropriate to compare the primary endpoint before and after 12 weeks of evolocumab therapy, and compare continuous secondary endpoints after 1 year of evolocumab therapy to baseline. A linear mixed model analysis will be conducted to analyze immunosuppression serum levels measured at baseline, 3 months, 6 months, 9 months, and 1 year of evolocumab therapy. The binary secondary endpoint of CAV progression will be assessed after 1 year of evolocumab therapy using McNemar tests. Safety data will be reported with frequencies and percentages. All tests will be two-tailed. A p-value <0.05 will be considered significant. Analysis will be performed using SAS version 9.4 (SAS Institute, Cary, NC).

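### Does Section 8 need to name a confidence interval for the week-12 LDL percentage change?

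*Combined protocol and SAP*

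**What the plan says.** The section headed Primary endpoint states an estimation aim: "The primary objective of this study is to measure the impact of PCSK9 inhibition via evolocumab on serum LDL". It adds that "LDL change will serve as the primary endpoint providing a direct benchmark for comparison of heart transplant" patients, by analogy with earlier evolocumab trials.

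Section 8 (Statistical Analysis Plan) defines the endpoint: "The primary outcome is percentage change from the baseline in LDL levels after 12 weeks of evolocumab therapy". The sizing statement is "The sample size of n=40 is expected to yield greater than 99% power to detect 50% reduction of LDL cholesterol from baseline", at a significance level of 0.05, "using a two-sided Wilcoxon signed-rank test, assuming the estimated standard deviation of reduction of 0.17". The analysis sentence reads "Paired t-tests or Nonparametric Wilcoxon signed-rank tests will be completed where appropriate to compare the primary endpoint before and after 12 weeks", and the decision rule is "A p-value <0.05 will be considered significant", two-tailed.

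Continuous variables are to be summarised by the mean with its standard deviation, "or median with range for continuous variables, unless otherwise indicated". Neither Section 8 nor any other part of the document mentions a confidence interval, a standard error or a target precision. Section 8 closes by treating the secondary endpoints as mainly hypothesis-generating, so week-12 LDL is the study's main result.

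**The concern.** The aim is to measure an effect, while the planned inference only asks whether the effect differs from zero. With the effect expected from prior trials, that question is almost settled in advance. A very small p-value would not tell a reader whether LDL fell by a quarter or by a half.

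The planned summaries do not state precision either. A standard deviation or a range describes how patients differ from one another, not how well the average change is known. If the signed-rank test is used and paired with a median and range, the main result could appear as a median, a range and a tiny p-value. A reader wanting to set the result beside the cited fall of more than 50% would not know whether the estimate is good to 5 points or to 10.

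**Working it through.** **Inputs.** From Section 8: n = 40, reduction 0.50, SD of the reduction 0.17, two-sided alpha 0.05, signed-rank test. Assumptions, because the document gives no dropout rate and no alternative SD: evaluable n of 36 or 30, and SD of 0.25 or 0.30.

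**1. The plan's power figure.** One-sample normal approximation, null of zero change: power = Φ(δ√n/SD − 1.96).

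- δ√n/SD = 0.50 × 6.325 / 0.17 = 18.60, and 18.60 − 1.96 = 16.64, so power is essentially 100%.
- With the worst-case efficiency of the signed-rank test (0.864), effective n = 40 × 0.864 = 34.56. Then 0.50 × 5.879 / 0.17 − 1.96 = 15.33, again essentially 100%.
- Simulation of the signed-rank test (20,000 normal samples) gives 1.000.

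The claim of more than 99% is correct.

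**2. What the test can tell apart.** The smallest observed mean fall that is significant by t-test at n = 40 and SD 0.17 is 2.023 × 0.17/√40 = 0.054, or 5.4 points. Simulated signed-rank power at a true fall of 25% is 1.000 at SD 0.17, 0.9999 at SD 0.25 and 0.9987 at SD 0.30 (n = 40), and 0.9963 at n = 36 with SD 0.30. At a true 50% fall with n = 40 it is 1.000 at all three SDs. The p-value therefore says little about size, and the premise of the concern holds.

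**3. The interval that is not named.** t-based half-width = t(0.975, n−1) × SD/√n. For the plan's own figures: 2.023 × 0.17/6.325 = 0.0544.

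| Evaluable n | SD 17% | SD 25% (assumed) | SD 30% (assumed) |
|---|---|---|---|
| 40 | 5.4 | 8.0 | 9.6 |
| 36 (assumed) | 5.8 | 8.5 | 10.2 |
| 30 (assumed) | 6.3 | 9.3 | 11.2 |

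Entries are percentage points. Around an observed fall of 50%, the first cell gives an interval of 44.6% to 55.4%.

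**4. Does the choice of interval matter?** The Hodges-Lehmann interval, which goes with the signed-rank test, has a simulated mean half-width of 5.5 points at n = 40 and SD 17%, against 5.4 for the t-based one. An interval for the sample median is about 1.96 × 1.2533 × 0.17/√40 = 0.066, or 6.6 points. If the changes are roughly normal, leaving the method to the analyst costs little.

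**5. Can a reader recover the interval from what is planned?**

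- *Mean with SD of the percentage change:* yes, by the formula in step 3.
- *Median with range:* only by assuming a distribution. At n = 40 and SD 17% the expected range is about 73 points (95% of simulated samples lie between 53 and 98). Under normality it averages 0.734/0.17 = 4.3 SDs, so it gives at best a rough guide to the SD.

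The loss is therefore confined to the second summary, and only if nothing is added to it.

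**The case for a change.** The strongest case for a change is that it costs nothing and suits the design. In a single-arm study whose size is set by the number of eligible clinic patients, precision is the natural statement of what 40 patients deliver. Section 8 also leaves both the test and the summary to be chosen where appropriate, so naming one estimator with its interval would remove some discretion. The permissive wording of the summary sentence does not itself promise an interval.

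All of that stands as a preference for fuller reporting. It does not show that the plan leads to a wrong or missing result:

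- A 95% interval needs no new data, endpoint, population or test. With a fall near 50%, discretion over its method could not turn a failure into a success, so fixing it in advance protects against little.
- The benchmark argument carries limited weight. Prior trials are cited only as showing more than 50%, an open-ended floor, and this is an uncontrolled cohort on mixed background lipid therapy. Any comparison stays descriptive, and an interval would cover sampling error only.
- Writing an expected precision into Section 8 would need care. The SD of 17% is itself an estimate, and quoting only 5.4 points would hide a plausible range reaching 9.6 at n = 40.
- An interval clause would not by itself settle the estimator. It would still depend on the open choice of test, and the before-and-after wording can be read as a comparison of LDL values as well as of per-patient percentage changes. The power inputs, a 0.50 reduction with SD 0.17, point to the latter.

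**Conclusion.** No change to the plan is needed. The document names no confidence interval, but this is a reporting detail that analysts fill sensibly. Followed as written, Section 8 gives an estimate of the week-12 LDL change, a valid test and a correctly powered comparison with zero. Adding the interval afterwards would not alter the conclusion.

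The missing figure is about ±5.4 points at the plan's SD of 17% with 40 evaluable patients. It rises to about ±9.6 at an assumed SD of 30%, and to about ±11.2 if in addition only 30 patients are evaluable. These sizes assume roughly normal percentage changes; the larger SDs and smaller counts are not in the document.

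The judgement also rests on the biostatistics faculty named in Section 8 reporting either the mean with SD, or a median accompanied by an interval. If the published result were a bare median and range, a reader would lose the precision but not the finding.

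### The secondary-endpoint text compares QCA change on evolocumab with the preceding year, but the only Section 8 rule that fits QCA is year 1 versus baseline, which leaves the prior-year film out of the test

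*Combined protocol and SAP*

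**What the plan says.** The CAV paragraph under Secondary endpoints introduces the measurement: "Percentage diameter stenosis for each vessel with visible CAV also will be determined by quantitative coronary angiography (QCA", read blinded on "patients angiograms completed one year prior to study entry, at study entry, and study conclusion". It states the comparison: "Angiographic change while on evolocumab therapy will be compared to the preceding year". The section closes by deferring the analysis: "Statistical analysis is detailed in Section 8 below".

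Section 8 (Statistical Analysis Plan) names neither QCA, nor stenosis, nor the preceding year. It offers three inferential rules for secondary endpoints:

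- Paired t or Wilcoxon signed-rank tests, where appropriate, to "compare continuous secondary endpoints after 1 year of evolocumab therapy to baseline".
- For drug levels: "A linear mixed model analysis will be conducted to analyze immunosuppression serum levels measured at baseline" and at four later times.
- For CAV grade: "The binary secondary endpoint of CAV progression will be assessed after 1 year of evolocumab therapy using McNemar tests".

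Its last paragraph treats conclusions from secondary endpoints as mainly hypothesis-generating.

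**The concern.** The study has a single cohort and no randomized control. For QCA, each patient's own preceding year is the only comparator that the documents name. The endpoint text asks whether stenosis grew more slowly on drug than before it. The Section 8 rule asks whether stenosis changed at all during the treatment year. These are different questions and can give opposite messages: a drug that halves progression can produce a significant worsening under Section 8, and a drug that stops progression produces no signal.

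If both tests stay available, the choice between them could be made after the results are seen. At stake is whether the QCA result can support a later study, which is the use Section 8 gives to secondary results.

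One further detail is open. The endpoint text does not say on which of the three films CAV must be visible for a vessel to be measured.

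**Working it through.** **Which rule applies.** Write P, B and Y for percent stenosis on the prior, entry and conclusion films.

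- Endpoint text: (Y − B) against (B − P).
- Section 8 mixed model: limited to immunosuppression levels.
- Section 8 McNemar test: limited to binary CAV progression.
- Section 8 paired rule: Y against B. P does not enter.

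Could baseline mean the prior-year change? The rest of the document points the other way. Baseline LDL is taken at enrollment. Lipids "after 52 weeks of evolocumab therapy will be compared to baseline levels". The mixed model lists baseline as a time point.

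**The plan's own figure.** No power is stated for QCA. The stated power above 99% for LDL does reproduce: 0.50/0.17 × √40 = 18.6 standard errors, so power is essentially 1. It has no bearing on QCA.

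**Inputs.** From the plan: n = 40, two-sided 0.05. Assumed, because the documents give no QCA variability or growth rate: patient-level SD of one year's change 5 or 8 points; growth of 4 or 2 points a year; share f of that change's variance due to reading error, 0 to 1; within-patient correlation r of true progression in the two years, 0 to 0.5.

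**Formulas.**

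- Section 8 test: noncentrality = mean(Y − B) / (SD/√40), 39 df. For mean 2 this is 2.53 (SD 5) or 1.58 (SD 8).
- Endpoint contrast: the entry film enters (Y − B) − (B − P) twice. With reading-error variance s² per film, a single change carries 2s² = f·SD², and the contrast carries (1 + 4 + 1)s² = 3f·SD². True progression adds 2(1 − f)(1 − r)·SD². So the contrast SD = SD × k, with k = √[2(1 − f)(1 − r) + 3f].
- k is smallest at f = 0, r = 0.5: √1 = 1.0. It is largest at f = 1: √3 = 1.73. At f = 0.5, r = 0 it is √2.5 = 1.58.

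**Probability of a significant result (noncentral t):**

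| True growth, year before → on drug | Section 8 test, SD 5 / SD 8 | Endpoint contrast, SD 5 | Endpoint contrast, SD 8 |
|---|---|---|---|
| 4 → 2 (halved) | 0.69 / 0.34 | 0.30–0.69 | 0.15–0.34 |
| 2 → 2 (no effect) | 0.69 / 0.34 | 0.05 | 0.05 |
| 4 → 4 (no effect) | 0.999 / 0.87 | 0.05 | 0.05 |
| 4 → 0 (stopped) | 0.05 / 0.05 | 0.81 to above 0.99 | 0.43–0.87 |

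Ranges run from k = 1.73 to k = 1.0. A middle case (f = 0.5, r = 0) gives 0.35 or 0.16 for halved and 0.88 or 0.50 for stopped. The first two rows carry the point: the Section 8 test cannot tell them apart. That holds for any SD, because the test does not contain P.

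**The case against.** The strongest reply is that the endpoint text already specifies the analysis. It gives the variable, three dated films, blinded reading and the comparison, and Section 8 supplies a paired test family to be used where appropriate. Two yearly changes in one patient are paired continuous data, and specific text would normally govern a general sentence. Otherwise the prior film would be read for nothing. Much of this stands. A reader might infer that the contrast has no pre-specified form, or that the earlier film will be ignored; the documents do not support either. But the endpoint text hands the analysis to Section 8, and Section 8 states a different comparison. The unit of analysis (vessel or patient) is also left open.

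A reader might also infer a known bias in favour of the drug, from two sources. The documents support a figure for neither.

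- Vessel choice. If visibility were judged on the entry film with error shared with the QCA reading, regression to the mean would flatter the drug. If the visual judgement is independent of QCA error, the bias is about zero. No visibility cut-off or error correlation is given.
- Old prior films. Standard post-transplant care lets catheterization alternate with stress echocardiography beyond five years, so a patient first diagnosed then may lack a film from one year before entry. But the endpoint text asks for a film one year before entry, so an older one is better counted as missing. Catheterization is annual once CAV is diagnosed, and the registration section reports over 40 patients with known CAV. The share affected is unknown and may be small.

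Finally, the stakes are limited: this is one component of a secondary endpoint in a small uncontrolled study. That lowers the priority but does not reconcile the two texts.

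**Conclusion.** The inconsistency is real and should be resolved. It rests on the text alone: the one Section 8 rule that can cover QCA omits the film on which the stated comparison depends, so it cannot separate slowed progression from progression that was always slow. The sizes above are illustrations under assumed SDs, growth rates, reading-error shares and correlations. No bias figure is claimed for film interval or vessel selection. The consequence is confined to a hypothesis-generating secondary result; the LDL primary analysis is not touched.

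**What to change.** In Section 8, exempt QCA from the year-1-versus-baseline rule and state:

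- The contrast: within each patient, (entry to conclusion change) minus (prior film to entry change), each expressed per year using the actual film interval.
- The analysis: paired t or Wilcoxon on patient-level values, or a mixed model with vessels nested in patient, reporting the estimate with a 95% CI.
- The vessel set: the same vessels on all three films, namely those with CAV visible on any of the three and not only on the entry film.
- The number of patients without a film from about one year before entry.

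The cost is a short paragraph in Section 8 and some extra vessel readings on films already planned. The statistical price is precision: the contrast SD is 1.0 to 1.73 times that of a single change under the assumptions above, so a modest slowing will often be missed. The interval estimate should therefore carry the interpretation.
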